9.2. Unanticipated Adverse Device Effects (UADE)

An unanticipated adverse device effect (UADE) is defined in 21 CFR 812.3(s) as any serious adverse effect on health or safety or any life-threatening problem or death caused by, or associated with, a device, if that effect, problem or death was not previously identified in nature, severity or degree of incidence in the investigational plan or protocol.

The Sponsor is required to notify FDA within (10) days of any unanticipated adverse device effect. The Sponsor is required to notify PMDA within (15) days of any unanticipated adverse device effect not resulting in death; the Sponsor is required to notify PMDA within (7) days of any unanticipated adverse device effect resulting in death or which may result in death. If a complication occurs that the Investigator believes may be a potential UADE, the Site should immediately contact the Sponsor to determine reporting requirements. In addition, when there is a reason to believe a device may have malfunctioned, causing potential harm to a patient, the Site should immediately notify the Sponsor.

The Investigator will submit to the reviewing IRB a report of any UADE occurring during an investigation as soon as possible, but in no event later than ten (10) days after the Investigator learns of the effect. All UADEs must be documented by the Investigator including the date of onset, a complete description of the event, possible reason(s) for the event, severity, duration, actions taken and outcome. Copies of all supporting documents should be submitted concurrently with the appropriate CRF.

A report from the Sponsor will be submitted to the FDA and to all reviewing IRBs and participating Investigators within 10 working days after the Sponsor first receives notice of the effect.

GORE CONFIDENTIAL INFORMATION

9.3. Data and Safety Monitoring Board

An independent Data and Safety Monitoring Board (DSMB) will oversee conduct of the study. The DSMB will review accumulating study safety data on a regular basis and will advise the Sponsor regarding the continuing safety of study subjects as well as the continuing validity and scientific merit of the study. The DSMB will be comprised of an interdisciplinary team of at least 3 members (2 voting physicians, and one voting statistician) with pertinent expertise in carotid stenting who are not directly involved in the conduct of the study. The members will be compensated for their involvement in the DSMB, including reimbursement for reasonable travel expenses to attend meetings.

This committee will operate under pre-specified procedures as outlined in the DSMB Charter in accordance with the FDA's Guidance for Clinical Trial Sponsors on the Establishment and Operation of Clinical Trial Data Monitoring Committees. The DSMB will be responsible for conducting periodic reviews of aggregate data on a prescribed basis. The frequency of data review and other roles and responsibilities of the DSMB will be specified in the DSMB Charter.

Based on the safety data review, the DSMB will make recommendations to the Sponsor. Recommendations may include study continuation with or without major or minor modifications, temporary suspension of enrollment and / or study intervention until some uncertainty is resolved. All final decisions regarding study modifications rest with the Sponsor.

[figure not shown]
9.4. Clinical Events Committee

An independent Clinical Events Committee (CEC) will review potential primary endpoint events and adjudicate events based on endpoint definitions in the study protocol. The CEC will be comprised of an interdisciplinary team with pertinent knowledge in carotid stenting or the cardiovascular and/or nervous system who are not directly involved in the conduct of the study. The members will be compensated for their involvement in the CEC, including reimbursement for reasonable travel expenses to attend meetings.

This committee will operate under pre-specified procedures as outlined in the CEC Charter. The adjudication process will be initiated after a potential primary endpoint event is reported by the site.

10. Statistical Analysis

[figure not shown]

[figure not shown]
CONFIDENTIAL INFORMATION MD133246 Protocol Template Revision#: 1 Doc Type: GC

GORE® Carotid Stent MD134865 GCS 10-08 PROT Revision#: 3 Doc Type: SP

10.4. Data Analysis

10.4.1. Timing of Analyses

The primary endpoint analysis will occur when enrollment and one year follow-up are complete. No interim analyses of the study hypotheses are planned.

10.4.2. Baseline Characteristics

Subject demographics, clinical history, risk factors, and preprocedure lesion characteristics will be summarized using descriptive statistics for continuous variables (mean, standard deviation, number of observations, minimum and maximum) and discrete variables (percentage and count/sample).

10.4.3. Analysis Sets

The primary endpoint will be analyzed both on an intent-to-treat basis and on a perprotocol basis. The primary analysis set for testing of the primary endpoint is the perprotocol analysis set.

Intent-To-Treat (ITT) Analysis Set

The ITT analysis set is defined as all enrolled subjects with adequate informed consent, regardless of whether the study stent was implanted. Because technical failures (test device attempted but not implanted) are followed only to 30 days, this set will be used in the analysis of safety endpoints (major, serious, and nonserious adverse events) to 30 days and secondary endpoints evaluated at procedure, discharge, and 30 days.

Per-Protocol Analysis Set (Primary Analysis Set)

For per-protocol analysis, only subjects who had the study stent implanted in the target vessel and had no major protocol deviations will be included in the analysis. Major protocol deviations are defined as protocol deviations with a level of seriousness such that inclusion of the subject(s) would unacceptably bias the primary endpoint analysis. An example of a major protocol deviation might be failure to satisfy eligibility criteria to a degree where the subject does not fit the underlying scientific model for the treatment.

The per-protocol set will be used for the primary analyses of the primary endpoint. Ideally, this analysis set will consist of all subjects from the ITT set with technical success (test device implanted).

The Per-Protocol set will be used in additional analyses of the primary and secondary endpoints.

The primary safety and efficacy endpoints will also be analyzed controlling for the following baseline covariates: age, sex, and race/ethnicity.

Additional subgroup analyses may be performed based on variables identified to be significant predictors (p-value<0.05) in multivariate analyses.

10.4.4. Pooling of Data

Site data will be pooled based on clinical comparability, i.e., the sites used a common protocol, the sponsor adequately monitored the study to assure protocol compliance, and the data gathering and validation mechanisms were the same across all study sites.

Analyses to justify pooling will include the following:

- The primary endpoint will be presented by institution.
- An assessment of the poolability of the sites using a 2-by-(number of sites) contingency table of MAE outcome versus site. Fisher's Exact Test will be used to assess homogeneity. Sites with fewer than five subjects will be combined based on geographic region.
- If the sites are found to be significantly heterogeneous with respect to the primary endpoint, additional analyses will be conducted to assess differences between sites in baseline and procedural variables that might explain differences in primary outcome.

10.4.5. Statistical Analysis of Primary Endpoint

The primary endpoint of 1-year MAE is subject-based. A one-sided 95.1% upper confidence bound will be calculated (using the standard error based on H₀) and compared to the prespecified performance goal. If this bound is less than the performance goal, then the primary endpoint is met and the GORE® Carotid Stent will have demonstrated acceptable performance. The *P* value for the corresponding one-sided normal approximation to the binomial test will be reported. The primary hypothesis test will use α =0.049 to ensure an overall Type-1 error rate ≤0.05.

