#### 4.2 Timing of Analyses

#### 4.2.1 Primary Endpoint Analysis

The primary endpoint analysis will occur when enrollment has been completed and primary endpoint status has been determined for all enrolled and implanted subjects (generally after the one-year follow-up has been completed).

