#### 4.3 **Primary Endpoint**

The primary endpoint of 1-year MAE will be calculated as a subject-based binomial proportion. The numerator will be the count of subjects who experience death, any stroke, or MI through 30 days post-index procedure, or ipsilateral stroke through one year (365 days) post-index procedure. The denominator will be the count of subjects free of MAE and with clinical follow-up of at least 335 days post-index procedure, plus the count of subjects in the numerator. Only MAE adjudicated by the CEC will be used in this analysis. Acceptable clinical follow-up includes the Subject Evaluation CRF, duplex ultrasound, modified Rankin scale, and NIHSS.

A one-sided 95.1% upper confidence bound will be calculated (using the standard error based on  $H_0$ ) and compared to the prespecified performance goal. If this bound is less than the performance goal, then the primary endpoint is met and the test device will have demonstrated acceptable performance. The *P* value for the corresponding one-sided normal

approximation to the binomial test will be reported. The primary hypothesis test will use  $\alpha$ =0.049 to ensure an overall Type-1 error rate  $\leq$ 0.05.

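### Does the uncorrected normal-approximation test at alpha 0.049 break the promised 5% cap on the overall type I error?

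*Protocol*

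**What the plan says.** Protocol 10.4.5 and SAP 4.3 give the same rule. "A one-sided 95.1% upper confidence bound will be calculated" from the null standard error and set against the performance goal. "If this bound is less than the performance goal, then the primary endpoint is met". The "value for the corresponding one-sided normal approximation to the binomial test will be reported". Alpha is 0.049, which matches the bound (1 − 0.951 = 0.049), and the stated purpose is "to ensure an overall Type-1 error rate" no greater than 0.05. The sections that can be read mention neither a continuity correction nor an exact test.

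The number analysed is known only at the end. Protocol 10.4.3 makes the per-protocol set primary: "only subjects who had the study stent implanted in the target vessel and had no major protocol deviations". SAP 4.3 then counts every subject with an MAE, but counts an MAE-free subject only "with clinical follow-up of at least 335 days post-index procedure". The analysis waits until "primary endpoint status has been determined for all enrolled and implanted subjects" (SAP 4.2.1). Protocol 10.4.1 and SAP 5.0 plan no interim test of the hypothesis.

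**The concern.** The test treats an event count as if it were continuous. The largest passing count can only step by whole events, so the exact type I error saws up and down as the number analysed changes. A nominal 0.049 leaves 0.001 of room, less than the height of the teeth. A value tuned to the planned number would not necessarily hold at the number obtained.

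This is the only confirmatory test; the secondary endpoints are descriptive. It supports the PMA submission, and a single event can decide it. If the cap fails at the realised number, the study could pass on a result that an exact recalculation would put above 0.05.

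**Working it through.** **Inputs.** Enrolment 312 (Protocol 3.1); alpha 0.049; z(0.951) = 1.6546; simple binomial null variance, since SAP 4.3 calls the endpoint a subject-based binomial proportion. The performance goal p0 is not visible, so the plan's own figure of at most 0.05 cannot be reproduced at its design values. Assumed ranges: p0 from 5% to 25% in 0.1-point steps, and n from 250 to 312, giving 201 × 63 = 12,663 pairs.

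**Step 1: exact size at a fixed n.** Pass if x < n·p0 − 1.6546·√(n·p0·(1−p0)). Exact size is P(X ≤ c), where c is the largest passing count and X ~ Binomial(n, p0).

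- Over the grid the mean is 0.0449, the maximum is 0.0563 (p0 = 5.5%, n = 255, c = 8), and 22.8% of pairs exceed 0.05.
- Every goal on the grid has some n above 0.05; the per-goal maximum is 0.0518–0.0563.
- At nominal 0.05 the share above 0.05 is 28.5%, so the step down to 0.049 removes only part of the excess.

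Worked example, p0 = 14%, n = 308, 33 events:

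- null standard error = √(0.14 × 0.86/308) = 0.01977
- bound = 0.10714 + 1.6546 × 0.01977 = 0.1399, below 0.14, so pass
- normal P = 0.0483; exact P = 0.0533; Clopper-Pearson 95% bound = 14.06%

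The arithmetic behind the concern is therefore right, conditional on n.

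**Step 2: the overall rate when n is random.** Let n ~ Binomial(312, q), independent of outcome, and average the exact size over n. The table gives the largest value over the 201 goals.

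| q evaluable | Maximum size | Goals above 0.05 |
|---|---|---|
| 0.85 | 0.0475 | none |
| 0.95 | 0.0478 | none |
| 0.99 | 0.0498 | none |
| 0.995 | 0.0502 | 1% |
| 0.998 | 0.0522 | 8% |
| 1.0 | 0.0552 | 22% |

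At q = 0.995 the expected number not evaluable is 312 × 0.005 = 1.6 subjects.

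**Step 3: the SAP 4.3 denominator.** Here n depends on outcome. A loss to follow-up, or a death between day 31 and day 334 without an earlier MAE, takes a non-event out of the denominator; an MAE stays in whenever it occurred. Assume that p0 is the true rate in all implanted subjects, that a fraction l is lost without regard to outcome, that half of MAEs occur late, and that half of those go unseen in lost subjects. A counted subject then has event probability

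p* = p0(1 − l/4) / [p0(1 − l/4) + (1 − p0)(1 − l)].

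For p0 = 14%:

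- l = 1%: 0.13965/(0.13965 + 0.8514) = 0.1409
- l = 5%: 0.13825/(0.13825 + 0.8170) = 0.1447

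The observed rate is pushed up, so passing is harder. In the example above, P(X ≤ 33) at n = 308 falls from 0.0533 to 0.0486 at l = 1% and 0.0327 at l = 5%.

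Over the grid (0.2-point steps in p0), still conditional on n:

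| Loss l | Maximum size | Pairs above 0.05 |
|---|---|---|
| 1% | 0.0533 | 2.3% |
| 2% | 0.0505 | 0.08% |
| 5% | 0.043 | none |
| 10% | 0.032 | none |

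Averaged over n as well, the maximum is about 0.050 at l = 0.5% (0.049–0.051, depending on the number implanted and how many events go unseen), 0.047–0.048 at 1% and about 0.035 at 5%.

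**Step 4: what an exact test would change.** An exact binomial test at 0.05 lowers the pass mark by one event at 22.8% of pairs and never raises it. Its mean size is 0.041 against 0.045 now. At p0 = 14% and a true rate of 9.05% (both assumed), mean power falls from 0.814 to 0.802; over goals of 5–25%, where the present test has 80% power, the loss is 0.9–2.2 points. In the example the limit would move from 33 events (size 0.0533) to 32 (size 0.0367). The exact test overshoots downwards by more than the present test overshoots upwards.

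**The case for a change.** The strongest case for a change is that a trial reports one P value at one realised n, and an average over numbers that did not occur does not protect that result. If n falls short of 312 only through failed implantation or major deviations, with every remaining subject evaluable, Step 1 applies in full. An exact rule removes the doubt in a sentence, and the planned worst-case and tipping-point analyses address missing outcomes, not approximation error.

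Part of this stands. At some realised n the exact size is above 0.05, and the documents' verb is stronger than the test can strictly bear. But what is promised is an overall rate, and neither document offers a guarantee at each n. Conditioning on n with event probability p0 is also not the right model under SAP 4.3, because n itself carries outcome information; for the same reason an exact test on that denominator would not hold its nominal level exactly either.

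The proposed move to 0.05 has its own risk. The reason for holding back 0.001 may lie in text that cannot be seen, and SAP 4.2.2 does describe a staged look at safety and efficacy results in the first 50 subjects, although no interim hypothesis test is planned.

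**Conclusion.** No change to the plan is needed. The rule is fully prespecified and leaves no choice to be made after the data are seen. Its mean exact size is 0.045 over the assumed ranges, its worst excess at any single n is about 0.6 of a percentage point, and only 0.3% of pairs exceed 0.055. As an overall rate the 0.05 cap holds in most realistic cases; it is exceeded by more than a trace only if nearly all implanted subjects are evaluable at one year, and then only for some values of the goal. Replacing the test would exchange a small, occasional excess for 1–2 points of power, which is a fair trade-off in either direction. Nothing prevents the analysts from showing the exact P value beside the prespecified one if the result falls within an event of the limit.

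This rests on an assumed goal of 5–25%, 250–312 evaluable subjects, simple binomial variance (the SAP writes the null hypothesis as a sum of two terms whose details cannot be read), and loss to follow-up that is unrelated to outcome apart from the denominator rule.

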10.4.6. Sensitivity Analyses

Sensitivity analyses of the primary endpoint will be conducted and will include, at a minimum, a worst-case analysis and tipping point analysis.

10.4.7. Statistical Analysis of Secondary Endpoint(s)

Secondary endpoints (subject-based unless otherwise specified) will be descriptive only; no formal statistical hypotheses will be tested. Secondary endpoints will be summarized at the specified time points using the descriptive statistics described above. No claims of statistical significance will be made based on secondary endpoint results. *P* values from these tests will not be reported in labeling, but may be used for scientific presentations and/or manuscripts.

10.5. Publication Plan

The International Committee of Medical Journal Editors (ICMJE) member journals have adopted a trials-registration policy as a condition for publication. This policy requires that all clinical trials be registered in a public trials registry. The Sponsor will register the study and post results as required by this policy and applicable U.S. laws and regulations.

It is the intent of the sponsor that the multicenter results of this study will be submitted for publication. A publications committee will be established to review the multicenter results and develop publications at the completion of the study. The timing of the multicenter publication may be dependent on regulatory submissions and approvals. Individual investigative sites should coordinate requests for publication through the publications committee or the sponsor.

11. Ethical and Regulatory Considerations

11.1. Statement of Compliance

The study will be conducted in compliance with this protocol, International Conference on Harmonization Good Clinical Practice E6 (ICH-GCP), and applicable local regulatory requirements.

o 11	5
21 CFR Part 11	Electronic Records; Electronic Signatures
21 CFR Part 50	Protection of Human Subjects
21 CFR Part 54	Financial Disclosure By Clinical Investigators
21 CFR Part 56	Institutional Review Boards
21 CFR Part 812	Investigational Device Exemptions
ICH-GCP E6	International Conference on Harmonisation Regulations Guideline For Good Clinical Practice

The following are applicable to this study:

11.2. Compliance Responsibilities

The Sponsor will conduct the clinical study in accordance with all applicable regulations and laws. The Sponsor will be responsible for documenting that Investigators have the necessary skills, training and information to properly conduct the clinical study. The Sponsor will ensure proper monitoring of the clinical study and ensure the Site has obtained IRB approval prior to enrollment. The Sponsor will provide information to the Investigators, the reviewing IRB and governing regulatory agencies concerning the progress and any new material information about the clinical study.

The Investigator will conduct the clinical study in accordance with all applicable regulations and laws, any relevant agreements, the study protocol, and all approval conditions of the reviewing IRB and governing regulatory agencies. The Investigator will ensure IRB approval is obtained prior to enrollment, maintained throughout the course of the study, and that all IRB reporting requirements are met. The Investigator is responsible for protecting the rights, safety, and welfare of subjects under the Investigator's care and for the control of devices under investigation. The Investigator is also responsible for ensuring that informed consent is properly obtained.

11.3. Informed Consent

The Investigator shall ensure that all potential subjects for this study are provided with a consent form describing this study and sufficient information to make an informed decision about their participation.

The formal consent of a subject, using the IRB-approved consent form, must be obtained by the Investigator before that subject undergoes any study procedure. The consent form will be signed and personally dated by the subject, and the person who conducted the informed consent discussion. The original signed informed consent form will be retained in the subject records. A copy of the informed consent document will be given to the subject for their records. Any significant, new information which emerges while the study is in progress that may influence a subject's willingness to continue to take part in the study will be provided.

The Investigator shall ensure that documentation of the acquisition of informed consent is recorded in each subject's records in accordance with applicable regulations.

11.4. Independent Ethical Review

The Investigator shall not enroll any subjects prior to obtaining approval for the study from a properly constituted independent IRB.

The Investigator will submit the protocol, informed consent forms, and other information to be provided to subjects, such as survey instruments or questionnaires, and any proposed advertising/recruitment materials for written approval.

11.5. Conflict of Interest

All Investigators will follow their Site's conflict of interest policies.

Investigators will provide Sponsor with sufficient accurate financial disclosure information to allow Sponsor to submit a complete and accurate certification or disclosure statement as required under 21 CFR 54, Financial Disclosure by Clinical Investigators. Investigators will promptly update this information if any relevant changes occur during the course of the investigation and for one (1) year following completion of the study.

Appendix A NIH Stroke Scale

ΝΙΗ	Patient Identification	
STROKE	Pt. Date of Birth / /	,
	Hospital()
SCALE	Date of Exam / /	
Interval: []Baseline []2 hours post treatment []3 months []Other	[] 24 hours post onset of symptoms ±20 minutes [] 7-10 days	
Time:: []am []pm		

Person Administering Scale _____

Administer stroke scale items in the order listed. Record performance in each category after each subscale exam. Do not go back and change scores. Follow directions provided for each exam technique. Scores should reflect what the patient does, not what the clinician thinks the patient can do. The clinician should record answers while administering the exam and work quickly. Except where indicated, the patient should not be coached (i.e., repeated requests to patient to make a special effort).

Instructions	Scale Definition	Score
1a. Level of Consciousness: The investigator must choose a response if a full evaluation is prevented by such obstacles as an endotracheal tube, language barrier, orotracheal trauma/bandages. A 3 is scored only if the patient makes no movement (other than reflexive posturing) in response to noxious stimulation.	 0 = Alert; keenly responsive. 1 = Not alert; but arousable by minor stimulation to obey, answer, or respond. 2 = Not alert; requires repeated stimulation to attend, or is obtunded and requires strong or painful stimulation to make movements (not stereotyped). 3 = Responds only with reflex motor or autonomic effects or totally unresponsive, flaccid, and areflexic. 	
1b. LOC Questions: The patient is asked the month and his/her age. The answer must be correct - there is no partial credit for being close. Aphasic and stuporous patients who do not comprehend the questions will score 2. Patients unable to speak because of endotracheal intubation, orotracheal trauma, severe dysarthria from any cause, language barrier, or any other problem not secondary to aphasia are given a 1. It is important that only the initial answer be graded and that the examiner not "help" the patient with verbal or non-verbal cues.	 0 = Answers both questions correctly. 1 = Answers one question correctly. 2 = Answers neither question correctly. 	
1c. LOC Commands: The patient is asked to open and close the eyes and then to grip and release the non-paretic hand. Substitute another one step command if the hands cannot be used. Credit is given if an unequivocal attempt is made but not completed due to weakness. If the patient does not respond to command, the task should be demonstrated to him or her (pantomime), and the result scored (i.e., follows none, one or two commands). Patients with trauma, amputation, or other physical impediments should be given suitable one-step commands. Only the first attempt is scored.	 0 = Performs both tasks correctly. 1 = Performs one task correctly. 2 = Performs neither task correctly. 	
2. Best Gaze: Only horizontal eye movements will be tested. Voluntary or reflexive (oculocephalic) eye movements will be scored, but caloric testing is not done. If the patient has a conjugate deviation of the eyes that can be overcome by voluntary or reflexive activity, the score will be 1. If a patient has an isolated peripheral nerve paresis (CN III, IV or VI), score a 1. Gaze is testable in all aphasic patients. Patients with ocular trauma, bandages, pre-existing blindness, or other disorder of visual acuity or fields should be tested with reflexive movements, and a choice made by the investigator. Establishing eye contact and then moving about the patient from side to side will occasionally clarify the presence of a partial gaze palsy.	 0 = Normal. 1 = Partial gaze palsy; gaze is abnormal in one or both eyes, but forced deviation or total gaze paresis is not present. 2 = Forced deviation, or total gaze paresis not overcome by the oculocephalic maneuver. 	

NIH STROKE SCALE

Patient Ider	ntification			
	Pt. Date of Birth	/	/	
Hospital		()
	Date of Exam	/	/	

Interval: [] Baseline [] 2 hours post treatment [] 24 hours post onset of symptoms ±20 minutes [] 7-10 days [] 3 months [] Other ______(____)

3. Visual: Visual fields (upper and lower quadrants) are tested by confrontation, using finger counting or visual threat, as appropriate. Patients may be encouraged, but if they look at the side of the moving fingers appropriately, this can be scored as normal. If there is unilateral blindness or enucleation, visual fields in the remaining eye are scored. Score 1 only if a clear-cut asymmetry, including quadrantanopia, is found. If patient is blind from any cause, score 3. Double simultaneous stimulation is performed at this point. If there is extinction, patient receives a 1, and the results are used to respond to item 11.	 0 = No visual loss. 1 = Partial hemianopia. 2 = Complete hemianopia. 3 = Bilateral hemianopia (blind including cortical blindness). 	
4. Facial Palsy: Ask – or use pantomime to encourage – the patient to show teeth or raise eyebrows and close eyes. Score symmetry of grimace in response to noxious stimuli in the poorly responsive or non-comprehending patient. If facial trauma/bandages, orotracheal tube, tape or other physical barriers obscure the face, these should be removed to the extent possible.	 0 = Normal symmetrical movements. 1 = Minor paralysis (flattened nasolabial fold, asymmetry on smiling). 2 = Partial paralysis (total or near-total paralysis of lower face). 3 = Complete paralysis of one or both sides (absence of facial movement in the upper and lower face). 	
5. Motor Arm: The limb is placed in the appropriate position: extend the arms (palms down) 90 degrees (if sitting) or 45 degrees (if supine). Drift is scored if the arm falls before 10 seconds. The aphasic patient is encouraged using urgency in the voice and pantomime, but not noxious stimulation. Each limb is tested in turn, beginning with the non-paretic arm. Only in the case of amputation or joint fusion at the shoulder, the examiner should record the score as untestable (UN), and clearly write the explanation for this choice.	 0 = No drift; limb holds 90 (or 45) degrees for full 10 seconds. 1 = Drift; limb holds 90 (or 45) degrees, but drifts down before full 10 seconds; does not hit bed or other support. 2 = Some effort against gravity; limb cannot get to or maintain (if cued) 90 (or 45) degrees, drifts down to bed, but has some effort against gravity. 3 = No effort against gravity; limb falls. 4 = No movement. UN = Amputation or joint fusion, explain: 5a. Left Arm 5b. Right Arm 	
6. Motor Leg: The limb is placed in the appropriate position: hold the leg at 30 degrees (always tested supine). Drift is scored if the leg falls before 5 seconds. The aphasic patient is encouraged using urgency in the voice and pantomime, but not noxious stimulation. Each limb is tested in turn, beginning with the non-paretic leg. Only in the case of amputation or joint fusion at the hip, the examiner should record the score as untestable (UN), and clearly write the explanation for this choice.	 0 = No drift; leg holds 30-degree position for full 5 seconds. 1 = Drift; leg falls by the end of the 5-second period but does not hit bed. 2 = Some effort against gravity; leg falls to bed by 5 seconds, but has some effort against gravity. 3 = No effort against gravity; leg falls to bed immediately. 4 = No movement. UN = Amputation or joint fusion, explain:	
	6b. Right Leg	J

NIH STROKE SCALE

Patient Id	lentification			
	Pt. Date of Birth _	/	/	
Hospital _		()
	Date of Exam _	/	/	

[figure not shown]
Interval: [] Baseline	[] 2 hours post treatment	[] 24 hours post onset of symptoms ±20 m	inutes [] 7-10 days
[] 3 months [] (Other	()	

7. Limb Ataxia: This item is aimed at finding evidence of a unilateral cerebellar lesion. Test with eyes open. In case of visual defect, ensure testing is done in intact visual field. The finger-nose-finger and heel-shin tests are performed on both sides, and ataxia is scored only if present out of proportion to weakness. Ataxia is absent in the patient who cannot understand or is paralyzed. Only in the case of amputation or joint fusion, the examiner should record the score as untestable (UN), and clearly write the explanation for this choice. In case of blindness, test by having the patient touch nose from extended arm position.	0 = Absent. 1 = Present in one limb. 2 = Present in two limbs. UN = Amputation or joint fusion, explain:	
8. Sensory: Sensation or grimace to pinprick when tested, or withdrawal from noxious stimulus in the obtunded or aphasic patient. Only sensory loss attributed to stroke is scored as abnormal and the examiner should test as many body areas (arms [not hands], legs, trunk, face) as needed to accurately check for hemisensory loss. A score of 2, "severe or total sensory loss," should only be given when a severe or total loss of sensation can be clearly demonstrated. Stuporous and aphasic patients will, therefore, probably score 1 or 0. The patient with brainstem stroke who has bilateral loss of sensation is scored 2. If the patient does not respond and is quadriplegic, score 2. Patients in a coma (item 1a=3) are automatically given a 2 on this item.	 0 = Normal; no sensory loss. 1 = Mild-to-moderate sensory loss; patient feels pinprick is less sharp or is dull on the affected side; or there is a loss of superficial pain with pinprick, but patient is aware of being touched. 2 = Severe to total sensory loss; patient is not aware of being touched in the face, arm, and leg. 	
9. Best Language: A great deal of information about comprehension will be obtained during the preceding sections of the examination. For this scale item, the patient is asked to describe what is happening in the attached picture, to name the items on the attached naming sheet and to read from the attached list of sentences. Comprehension is judged from responses here, as well as to all of the commands in the preceding general neurological exam. If visual loss interferes with the tests, ask the patient to identify objects placed in the hand, repeat, and produce speech. The intubated patient should be asked to write. The patient in a coma (item 1a=3) will automatically score 3 on this item. The examiner must choose a score for the patient with stupor or limited cooperation, but a score of 3 should be used only if the patient is mute and follows no one-step commands.	 0 = No aphasia; normal. 1 = Mild-to-moderate aphasia; some obvious loss of fluency or facility of comprehension, without significant limitation on ideas expressed or form of expression. Reduction of speech and/or comprehension, however, makes conversation about provided materials difficult or impossible. For example, in conversation about provided materials, examiner can identify picture or naming card content from patient's response. 2 = Severe aphasia; all communication is through fragmentary expression; great need for inference, questioning, and guessing by the listener. Range of information that can be exchanged is limited; listener carries burden of communication. Examiner cannot identify materials provided from patient response. 3 = Mute, global aphasia; no usable speech or auditory comprehension. 	
10. Dysarthria: If patient is thought to be normal, an adequate sample of speech must be obtained by asking patient to read or repeat words from the attached list. If the patient has severe aphasia, the clarity of articulation of spontaneous speech can be rated. Only if the patient is intubated or has other physical barriers to producing speech, the examiner should record the score as untestable (UN), and clearly write an explanation for this choice. Do not tell the patient why he or she is being tested.	 0 = Normal. 1 = Mild-to-moderate dysarthria; patient slurs at least some words and, at worst, can be understood with some difficulty. 2 = Severe dysarthria; patient's speech is so slurred as to be unintelligible in the absence of or out of proportion to any dysphasia, or is mute/anarthric. UN = Intubated or other physical barrier, explain: 	

NIH STROKE SCALE

Interval: [] Baseline [] 2 hours post treatment [] 24 hours post onset of symptoms ±20 minutes [] 7-10 days [] 3 months [] Other ______(___)

11. Extinction and Inattention (formerly Neglect): Sufficient information to identify neglect may be obtained during the prior	0 = No abnormality.	
testing. If the patient has a severe visual loss preventing visual double simultaneous stimulation, and the cutaneous stimuli are normal, the score is normal. If the patient has aphasia but does appear to attend to both sides, the score is normal. The presence of	 1 = Visual, tactile, auditory, spatial, or personal inattention or extinction to bilateral simultaneous stimulation in one of the sensory modalities. 	
visual spatial neglect or anosagnosia may also be taken as evidence of abnormality. Since the abnormality is scored only if present, the item is never untestable.	 2 = Profound hemi-inattention or extinction to more than one modality; does not recognize own hand or orients to only one side of space. 	

[figure not shown]
You know how.

Down to earth.

I got home from work.

Near the table in the dining room.

They heard him speak on the radio last night.

FIFTY – FIFTY THANKS HUCKLEBERRY BASEBALL PLAYER

MAMA

TIP – TOP

